16.3 Data Safety Monitoring Board

An independent DSMB will be established prior to study initiation. The committee will consist of at least two physicians (cardiologists) and a statistician who are not otherwise associated with the study, and who are experienced in HF multicenter trials.

The main tasks of the Board will be to provide recommendations to the Sponsor concerning safety aspects and study continuation/discontinuation within a cohort and from one cohort to the next one. If a cohort is stopped, the randomisation will be ended and the study treatment will be prematurely discontinued in patients on treatment. Escalation to the next dose level will not take place.

After the completion of cohort I, a safety interim analysis will be performed and the DSMB members will evaluate the incidence of troponin (cTnT) elevation. At interim analysis, the DSMB may recommend to stop the cohort if the incidence of troponin elevation is found to be statistically significantly higher on the istaroxime dose than on placebo, or if this difference is deemed to be clinically relevant. Consequently, the clinical study will be prematurely terminated. Randomization data and datasets needed to conduct the interim analysis will be given to the DSMB statistician. The DSMB will be unblinded when performing the interim analysis. During the interim analysis, DSMB members will analyze and discuss the results in closed

sessions. The DSMB is required to keep confidential and undisclosed until study conclusion: i) these discussions, ii) the detailed minutes thereof, and iii) the interim analysis results. At study conclusion, after database lock and unblinding, the DSMB will make the minutes and interim analysis results available as part of the study documentation.

Members of the DSMB will be:

[name] - Chairman of the DSMB

Head of Centro Ricerche Associazione Nazionale Medici Cardiologi (ANMCO) Firenze – Italy

[name] - Member of the DSMB as Physician

Scientific Director GVM Care and Research Unit Maria Cecilia Hospital Ravenna- Italy

[name] – Member of the DSMB as Statistician

Unità of Pharmacology "Giorgio Segre" – Siena University Siena - Italy

17. ETHICS

Prior to the starting of the trial, the study protocol, informed consent form and other materials for the patients should be submitted to the ethics committee of the responsible study center for approval. Sponsor must obtain the signed and approval document from the ethics committee before starting the study. Any amendments of the protocol and ICF should be approved by the EC. ICF should be signed again if necessary.

Investigator should obtain patient's informed consent and the signed ICF before implementation. Ensure patients' rights and keep confidential to patients' information throughout the study.

18. RESPONSIBILITY AND PUBLICATION

Investigator should keep confidential all information provided by sponsor. Other staff participating in the study and ethics committee should keep confidential the information as well. Without the written permission, the information cannot be provided to others.

All data and results of the clinical study are possessed by sponsor and investigator. Investigator agrees not to submit the results of this study for publication or presentation before the sponsor review the accuracy and no leakage of confidential information in the manuscript.

Protocol N°: CVT-CV-002

19. ANTICIPATED PROGRESS AND COMPLETION DATE OF THE STUDY

Procedure	Time	Working Time
Final version of study protocol, ICF and		
CRF		
Approval document of ethics committee		
Initial meeting and articles delivery of each		
center		
The first subject into screening		
The last subject enrolled		
The last subject finishing efficacy		
observation		
The collection of CRF		
Statistics analysis report		
Clinical report		
Summing-up meeting		
Anticipated completion date		

22. APPENDICES

22.1 Appendix A: Istaroxime Infusion Rate

Reconstitute 4 vials with 5 mL of saline each every 6 hours, draw into one single 50 mL syringe, remove 30 ml of saline from the NaCl 0.9% bag with the same syringe used for the reconstitution of the 4 vials in order to obtain a total volume of 50 ml (20 ml of the 4 vials+30 ml of saline the NaCl 0.9% bag) and infuse at the following rate (according to the precision of the electrical syringe of about 0.1 mL per hour).

PATIENT WEIGHT (kg)	INFUSION RATE (ml/h)	PATIENT WEIGHT (kg)	INFUSION RATE (ml/h)	PATIENT WEIGHT (kg)	INFUSION RATE (ml/h)
35	2.6	57	4.3	79	5.9
36	2.7	58	4.3	80	6.0
37	2.8	59	4.4	81	6.0
38	2.8	60	4.5	82	6.1
39	2.9	61	4.6	83	6.2
40	3.0	62	4.7	84	6.3
41	3.0	63	4.7	85	6.3
42	3.2	64	4.8	86	6.4
43	3.2	65	4.9	87	6.5
44	3.3	66	5.0	88	6.6
45	3.3	67	5.1	89	6.7
46	3.5	68	5.1	90	6.7
47	3.5	69	5.2	91	6.8
48	3.6	70	5.2	92	6.9
49	3.6	71	5.3	93	7.0
50	3.7	72	5.4	94	7.0
51	3.8	73	5.5	95	7.1
52	3.9	74	5.5	96	7.2
53	4.0	75	5.6	97	7.2
54	4.0	76	5.7	98	7.3
55	4.1	77	5.8	99	7.4
56	4.2	78	5.8	>100	7.5

# LIST OF ABBREVIATIONS

A Pick mitral flow velocity during atrial contraction

ADR Adverse Drug Reaction

AE Adverse Event

Ae Amount excreted unchanged into urine

Ae% Percent of the dose excreted unchanged into urine

ANCOVA Analysis of Covariance ANOVA Analysis of Variance

ATC Anatomical Therapeutic Chemical

AUC Area under the curve

AUC0-∞ Area under the concentration-time curve extrapolated to infinity

AUC0-t Area under the curve over the time interval 0 to the time of last quantifiable

concentration

BNP Brain Natriuretic Peptide CI Confidence interval ClR Renal clearance

Cmax Maximum concentration
CRF Case Report Form
CS Clinically Significant

cTnT Cardiac Troponin T
DMC Data Monitoring Committee

E Pick mitral flow velocity during early rapid filling
Ea Early diastolic myocardial relaxation velocity
E/Ea ratio for estimation of LV filling pressure
E/A ratio of the early over late filling velocity

ECG Electrocardiogram

eGFR Estimated glomerular filtration rate

EMEA European Medicines Agency

ICH International Conference on Harmonisation

ITT Intention-to-treat LV Left Ventricular

LVEF Left Ventricular Ejection Fraction

λz Terminal rate constant

MedDRA Medical Dictionary for Regulatory Activities
MMRM Mixed Models for Repeated Measures

NCS Not Clinically Significant

NR No result

NT-proBNP N-terminal prohormone brain natriuretic peptide

PK Pharmacokinetics
PP Per protocol

PR Interval between P and R waves

PT Preferred Term

QRS Interval between the beginning of Q wave and the end of S wave

1.0/30/10/2018 Page 5 of 28

QT Interval between the beginning of Q wave and the end of T wave

RR Interval between R and R waves
Sa Systolic myocardial velocity

SAE Serious adverse event SAP Statistical Analysis Plan SAS Statistical Analysis Systems

SD Standard deviation SOC System Organ Class SVI Stroke Volume Index t1/2 Terminal half-life

Tmax Time to maximum concentration TEAE Treatment-emergent adverse event

URL Upper Reference Limit

Vss Volume of distribution at steady-state

VAS Visual Analog Scale

Vz Volume of distribution during the terminal phase WHO-DD World Health Organization Drug Dictionary

1.0/30/10/2018 Page 6 of 28

#### 1.0 INTRODUCTION

This document outlines the statistical methods to be implemented in the analysis of the data of CVT-CV-002 Clinical Trial. The purpose of this plan is to provide general guidelines from which the analysis will proceed, containing a more technical and detailed elaboration of the principal features of the analysis described in the protocol. Any changes to the protocol or Case Report Form (CRF) may necessitate updates to the Statistical Analysis Plan (SAP). In case of deviations from this updated SAP, explanations will be provided in the clinical study report.

Relevant applicable CROS NT quality document will be followed also according to the contract with the Client.

# 1.1 CHANGES FROM PROTOCOL

The analysis of echocardiographic parameters is changed from the protocol:

- The analysis of echocardiographic parameters will be performed separately for each cohort, instead of performed on the combined cohorts.
- An analysis of variance (ANOVA) model with treatment as covariate is now the primary analysis, instead of a mixed model for repeated measures (MMRM) including treatment and additional covariates.
- Missing response data will not be imputed in the ANOVA analysis.

The justification for these changes are documented in the Memo to File prepared by [name], dated 24Oct2018, entitled: Change in analysis of echocardiographic parameters.

#### 2.0 VERSION HISTORY

Version	Summary/Reason for changes	Date Issued	
Number		to Client	
Draft 1	Draft specification based on:		
	• Study protocol (general protocol amendment no.1, 08 April 2013)	02 September 2013	
	• CRF (Version Final 2, 23 July 2013)		
Draft 2	The following change has been implemented after sponsor's		
	revision:	15 October	
	• The echocardiographic parameters to be considered in the global test have been defined.	2013	
Final 1.0	The following change has been implemented after sponsor's		
	revision:	30 October	
	The analysis of echocardiographic parameters is changed to an analysis of variance using only treatment as covariate.	2018	

1.0/30/10/2018 Page 7 of 28

#### 3.0 STUDY OBJECTIVES AND ENDPOINTS

# 3.1 STUDY OBJECTIVES

# 3.1.1 Primary Objective

The primary objective of this study is to evaluate the efficacy of two different doses of istaroxime (0.5 and 1.0  $\mu$ g/kg/min) in comparison with placebo on the E/Ea ratio in patients with Acute Decompensated Heart failure.

# 3.1.2 Secondary Objectives

To assess the safety, tolerability and efficacy of two different doses of istaroxime (0.5 and 1.0  $\mu g/kg/min$ ) in comparison with placebo, including cardiovascular and renal tolerability, as well as changes in biological markers such as N-terminal prohormone brain natriuretic peptide (NT-proBNP) and cardiac troponin T (cTnT), in two cohorts, Chinese and Italian/Caucasian patients with Acute Decompensated Heart failure.

In all the Italian patients and in a subset of Chinese patients pharmacokinetics (PK) and metabolism of istaroxime shall also be studied.

# 3.2 STUDY ENDPOINTS

# 3.2.1 Primary Endpoint

• The primary efficacy endpoint is the change from baseline to 24 hours after infusion start (treatment period Day 1) in the E/Ea ratio assessed by tissue Doppler.

# 3.2.2 Secondary Endpoints

The secondary efficacy endpoints are the following:

- Change from baseline to 24 hours in the treatment period Day 1 (addressing the differences between the changes at 6 and 24 hours from baseline) of the following Echo-Doppler parameters:
  - o Left Ventricular Ejection Fraction (LVEF)
  - o LV end systolic and end diastolic volumes
  - o Stroke volume index (SVI), and CI
  - o E, A and E/A ratio
  - o Ea and TAPSE
- Change from baseline to 24 hours in the E/Ea ratio assessed by tissue Doppler (difference between the changes at 6 and 24 hours from baseline)
- Others tissue doppler parameters such as Sa;
- Changes in dyspnoea assessed at 3, 6, 12, 24, 48 hours after infusion start by Visual Analog Scale (VAS) (including only patients presenting dyspnoea at baseline);

1.0/30/10/2018 Page 8 of 28

- Area under the curve (AUC) on changes in dyspnoea assessed at 3, 6, 12, 24, 48 hours after infusion start by VAS (including only patients presenting dyspnoea at baseline);
- Changes in Brain Natriuretic Peptide (BNP) from baseline at 24 hours;
- Proportion of patients with hospital readmissions or emergency visits for cardiovascular reasons by Day 30;
- Proportion of patients with episodes of worsening heart failure defined by the need to increase the dose or reinitiate i.v. therapy with diuretics and/ or other inotropic agents during the hospitalization;
- Length of hospitalization.

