14.2 Statistic Plan

All statistical analyses will be performed using Statistical Analysis Systems (SAS®) Software

(release 9.2) on a Windows 7 pro operating system.

Sample size

Protocol N°: CVT-CV-002

49

No formal sample size calculation has been calculated since there is no preliminary study to evaluate these endpoints at 24 hours after the infusion start.

In a previous study [14], there was a statistically significant decrease of the primary efficacy endpoint with istaroxime $0.5 \mu g/kg/min$ respect to placebo at 6 hours (twenty-nine patients in both groups). Since this study will investigate the primary efficacy endpoint at 24 hours and it is supposed that the profile at 24 hours should be similar to the one at 6 hours, it is expected that forty patients per group will be sufficient to evaluate a potential difference between istaroxime groups and placebo group on the primary efficacy endpoint at 24 hours.

Descriptive statistics

Descriptive statistics will be provided for each variable in summary tables by treatment group. Quantitative variables will be summarized by using n (sample size), mean, 95% confidence interval (CI) of the mean, median, standard deviation, minimum and maximum. Categorical variables will be summarized by using frequency count and percent distribution.

Principles of statistical analysis

For quantitative efficacy and safety variables, analysis within treatment groups will be presented. Mean changes from baseline and their 95% CIs will be calculated.

For all inferential analyses, p-value will be rounded to three decimal places. Statistical significance will be declared if the rounded p-value will be less than or equal to 0.05.

Subject's accountability

Disposition of patients, patient status and patients excluded from populations will be summarized by treatment group.

Description of the population-description of baseline characteristics

Descriptive statistics will be presented at baseline for demographic and baseline characteristics for the ITT population.

Primary efficacy endpoint

The primary efficacy endpoint (change from baseline in E/Ea ratio) will be analyzed using a linear mixed model for repeated measures including treatment, centre, timepoint, gender, baseline cTnT (normal <URL, abnormal ≥URL), atrial fibrillation (Yes/No) and treatment*timepoint interaction as fixed effects and baseline and baseline*timepoint interaction as covariates.

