# 4.1 SAMPLE SIZE

No formal sample size calculation has been calculated since there is no preliminary study to evaluate these endpoints at 24 hours after the infusion start.

In a previous study (Gheorghiade M. et al. Haemodynamic, echocardiographic, and neurohormonal effects of Istaroxime, a novel intravenous inotropic and lusitropic agent: a randomized controlled trial in patients hospitalized with heart failure. J Am Coll Cardiol. 2008; 51(23): 2276-85), there was a statistically significant decrease of the primary efficacy endpoint with istaroxime 0.5 µg/kg/min respect to placebo at 6 hours (twenty-nine patients in both groups). Since this study will investigate the primary efficacy endpoint at 24 hours and it is supposed that the profile at 24 hours should be similar to the one at 6 hours, it is expected that forty patients per group will be sufficient to evaluate a potential difference between istaroxime groups and placebo group on the primary efficacy endpoint at 24 hours.

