#### 7.7 ANALYSIS OF EFFICACY

# 7.7.1 Primary efficacy endpoint

Analysis will be performed separately for each cohort on ITT and PP populations.

E/Ea ratio will be summarized at each timepoint by treatment group by means of descriptive statistics.

Comparisons between treatment groups will be done using an ANOVA with change from baseline in E/Ea at 24 hours as dependent variable, and treatment as covariate.

The number of patients and the number of patients considered in the model will be provided by treatment. P-values of the fixed effects and covariates will also be presented.

The adjusted means for treatments and 95% CIs will be presented. The difference between the adjusted means for Istaroxime groups versus Placebo will be calculated with the 95% CIs and p-values.

The primary comparison will be Istaroxime 0.5  $\mu$ g/kg/min versus Placebo at 24 hours based on Cohort 1 subjects only. Highest dose of Istaroxime (1.0  $\mu$ g/kg/min) versus Placebo will be tested as a secondary comparison based on Cohort 2 subjects only.

The same analysis will be repeated for change from baseline in E/Ea at 6 hours. All treatment comparisons at 6 hours will be secondary analyses.

E/Ea ratio will also be summarized separated by cohort at each timepoint by treatment group by means of descriptive statistics.

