# Echocardiographic parameters

The following secondary endpoints:

o LVEF

1.0/30/10/2018 Page 19 of 28

- o LV end systolic and end diastolic volumes
- o SVI, and CI
- o E, A, E/A ratio
- Sa (tissue doppler parameters)
- o Ea and TAPSE

will be summarized at each timepoint by treatment group by means of descriptive statistics.

Comparison between treatment groups will be done using the ANOVA similar to the one used for the primary efficacy endpoint. Only change from baseline echocardiographic data at 6 hours and 24 hours values will be analyzed.

The global test using multivariate analysis of variance (MANOVA) considering multiple echocardiographic parameters will also be performed separately at 6 and 24 hours and by cohort for echocardiographic parameters grouped into 3 types of cardiac mechanics:

- Relaxation parameters such as: E/Ea, Ea
- Contraction parameters such as: Sa, TAPSE
- Overall cardiac pumping ability parameters such as: SVI, CI

The MANOVA p-value from Pallai's Trace will be reported. ((Olson (1976) suggests that Roy's largest root is too likely produce Type I errors and should be avoided, that Wilk's lambda and Hotelling's trace are sensitive to violations of equal covariances in smaller samples, and he recommends Pillai's trace for general use.)

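### The change in treatment effect between 6 h and 24 h is a listed secondary endpoint (clearly for E/Ea), but no analysis in the SAP estimates it

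*SAP*

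**What the plan says.** **Endpoint.** SAP 3.2.2 already has the 24 h change in E/Ea as the primary endpoint (3.2.1). It then lists a secondary E/Ea endpoint qualified as the "difference between the changes at 6 and 24 hours from baseline". The protocol lists it too, in the synopsis and in sections 6.1 and 14.2; the synopsis gives the E/Ea difference as an item of its own. For LVEF, the LV volumes, SVI, CI, E, A, E/A, Ea and TAPSE, the SAP endpoint is the 24 h change, "addressing the differences between the changes at 6 and 24 hours from baseline) of the following Echo-Doppler parameters".

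**Protocol model.** Protocol 14.2 planned a repeated-measures model with "treatment*timepoint interaction as fixed effects and baseline and baseline*timepoint interaction as covariates".

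**SAP model.** SAP 1.1 makes an ANOVA the primary analysis of the echocardiographic parameters, "instead of a mixed model for repeated measures (MMRM) including treatment and additional covariates", and analyses the cohorts separately. SAP 7.7.1 specifies for the primary endpoint an "ANOVA with change from baseline in E/Ea at 24 hours as dependent variable, and treatment as covariate", and then: "The same analysis will be repeated for change from baseline in E/Ea at 6 hours". For the other echocardiographic parameters SAP 7.7.2 states: "Only change from baseline echocardiographic data at 6 hours and 24 hours values will be analyzed". The MANOVA is also run separately at each time.

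**Sample size.** SAP 4.1 rests the choice of numbers on a 6 h result from an earlier study: "it is supposed that the profile at 24 hours should be similar to the one at 6 hours".

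**The concern.** A listed endpoint should have an analysis that produces it. For E/Ea the bracketed difference cannot simply be the 24 h change, because that is the primary endpoint. It must mean a comparison of the two times. The protocol's model contained the term needed for that comparison. The SAP's replacement does not, and its section on changes from the protocol does not mention the consequence.

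The quantity also has a use. The sample-size reasoning carries a 6 h finding over to 24 h by supposing similar profiles, and the 6 h to 24 h difference is the listed endpoint that examines this supposition within the trial. Without it, a reader has two separate results to compare. A significant result at one time and a non-significant one at the other is not evidence that the effect changed.

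**Working it through.** **Step 1. Does anything in the SAP estimate the difference?**

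| Place in SAP | What it provides | Gives the 24 h minus 6 h effect? |
|---|---|---|
| 6.3 Efficacy variables | Derivations for dyspnoea AUC and length of stay only | No |
| 7.7.1 | E/Ea ANOVA at 24 h, repeated at 6 h | No, two separate fits |
| 7.7.2 Echocardiographic parameters | Same ANOVA for the others; MANOVA at each time | No |
| 7.7.2 Dyspnoea | MMRM with treatment by time | Yes, but for dyspnoea only |
| 7.9 Other planned analysis | None | No |
| 9.0 ANOVA and MANOVA code | Treatment as the only model term, no repeated statement | No |

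The separate 95% CIs at 6 h and 24 h cannot be combined into a CI for the difference, because the correlation between the two times within patients is not reported.

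**Step 2. What would the estimate be?** Baseline cancels: D = change at 24 h − change at 6 h = E/Ea(24 h) − E/Ea(6 h). If each change has standard deviation SD and their correlation is r, then SD(D) = SD × √(2(1 − r)).

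**Step 3. Precision of D within a cohort.** Inputs: 40 active and 20 placebo (SAP 4.0); t(0.975, 58 df) = 2.002. The correlation r is not in the documents, so a range is shown.

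Half-width of the 95% CI = 2.002 × √(1/40 + 1/20) × √(2(1 − r)) × SD = 0.548 × √(2(1 − r)) × SD.

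| r | √(2(1 − r)) | Half-width, in SDs of a single-time change |
|---|---|---|
| 0.3 | 1.183 | 0.65 |
| 0.5 | 1.000 | 0.55 |
| 0.7 | 0.775 | 0.42 |
| 0.9 | 0.447 | 0.25 |

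A single-time comparison has half-width 0.55 SD. D is more precise than that only if r exceeds 0.5.

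**Step 4. Why two p-values do not stand in for D.** Suppose the true effect is the same at both times and each test has power p. With bivariate normal test statistics, P(exactly one significant) = 2 × (p − P(both)). At p = 0.55:

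| r | P(both) | P(exactly one significant) |
|---|---|---|
| 0.3 | 0.350 | 2 × (0.55 − 0.350) = 0.40 |
| 0.5 | 0.385 | 2 × (0.55 − 0.385) = 0.33 |
| 0.7 | 0.4245 | 2 × (0.55 − 0.4245) = 0.25 |
| 0.9 | 0.479 | 2 × (0.55 − 0.479) = 0.14 |

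**Step 5. Is 55% power a sensible value to illustrate with?** The plan states no power, effect size or SD, so there is no figure to reproduce. Protocol 1.2 reports −3.8 with p = 0.03 for E/Ea at the lower dose at 6 h, and SAP 4.1 gives 29 patients in both groups. Reading −3.8 as a between-group difference (an assumption; the text does not say):
- SE = 3.8 / 2.227 (t on 56 df) = 1.71
- SD = 1.71 / √(2/29) = 6.5
- SE with 40 v 20 = 6.5 × √0.075 = 1.78
- Power for 3.8 units is then about 57%.

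The result moves with the assumed power. At 90% power and r = 0.9, the chance of exactly one significant result falls to 0.06.

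**The case against.** **The stronger reading.** A reader might infer that persistence of effect to 24 h is never tested. The documents do not support that. The 24 h comparison with placebo is the primary test, and 6 h is a secondary one. What is missing is narrower: an estimate of how the effect changes between the two times.

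**The restricting sentence.** The SAP 7.7.2 sentence limiting the analysis to 6 h and 24 h may only exclude the 48 h echocardiogram, which protocol section 8 treats as exploratory. That is a fair reading, so the sentence should not be taken as ruling the difference out. It does not supply the difference either.

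**The other parameters.** For these the endpoint is worded as the 24 h change, which is analysed, with 6 h beside it. A formal comparison of the times is a possible reading but not a compelled one. This stands: only E/Ea is clear.

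**The protocol.** It wrote out no 6 h versus 24 h contrast, so no explicit analysis was deleted. This also stands. The model that could have yielded the contrast was removed, and nothing took its place.

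**The sample-size premise.** SAP 4.1 supposes similar profiles, not equal effects, so D is relevant to the premise without being a strict test of it.

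**Unseen papers.** The memo justifying the change and the table mock-ups are not among the documents. An analysis, or a deliberate decision to drop the endpoint, could be recorded there. The SAP text and code contain neither.

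**Conclusion.** The point holds as a gap between a listed endpoint and the analyses specified. Following the SAP as written leaves the 6 h to 24 h difference in E/Ea unestimated, and SAP 1.1 does not say that it was dropped. For the other Echo-Doppler parameters the wording is loose enough that the SAP should say what is meant. This conclusion rests on the text alone and needs no assumed number.

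The size of the interpretive problem does rest on assumptions. At 55% power and correlations of 0.3 to 0.7, two equal true effects give exactly one significant result in about 40% to 25% of trials.

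The matter is minor in rank. It concerns a secondary endpoint and leaves the primary comparison untouched. The missing estimate would have only modest precision, with a half-width of about 0.65 to 0.42 SD over the same correlations.

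**What to change.** 1. In SAP 6.3, derive D = E/Ea(24 h) − E/Ea(6 h) for each patient with both values. In 7.7.1, analyse D by treatment within each cohort with the same model as the primary endpoint, and report the difference from placebo with its 95% CI. Taking the treatment by time contrast from a by-cohort MMRM is an acceptable alternative.
2. Label the result a descriptive secondary estimate. State that a non-significant D is not proof of a maintained effect; that claim would need a margin, and the plan sets none.
3. For the other listed echocardiographic parameters, either do the same or reword the endpoint as changes at 6 h and at 24 h, and record the change in SAP 1.1.

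The cost is SAP wording, one derived variable per parameter and a repeat of existing code, with no new data. The downside is more secondary estimates of modest precision with no multiplicity control: E/Ea plus the ten other parameters, in two cohorts, makes 11 × 2 = 22 if all are done. Restricting the addition to E/Ea and rewording the rest keeps it to two.
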